### **3.2 Study Population**

The study population includes recipients of kidney allografts, no more than 14 days after transplantation and prior to discharge.

### **3.3 Criteria for Evaluation**

Primary efficacy endpoints:

The primary endpoint of this study will be the time to a composite event, which is defined as the time to first occurrence of acute rejection, or graft failure, or death. The definition of graft failure includes re-transplant, return to dialysis, and/or death. The definition of acute rejection will be based on the Banff 2007 classification. For power considerations, it is assumed that overall 13% of subjects will experience this endpoint by one year post-transplant.

Secondary efficacy endpoints:

Secondary efficacy endpoints will include individual analyses of graft rejection, failure, death, or loss-to-follow-up at 1 year after transplantation. The cause of graft failure and death will also be analyzed. In addition, these individual endpoints and the composite endpoint will be evaluated by age group (adult and elderly (>65) and ethnicity. Other endpoints will include, rejection severity, death due to organ failure, and medication adherence. Adherence will be measured with daily medication diaries, and with the coefficient of variation of tacrolimus in subjects' blood.

Secondary safety endpoints:

Secondary safety endpoints will include the need for hospitalization, infectious episodes (bacterial, fungal, and viral), development of malignancy, and development of new-onset diabetes after transplantation.

### 3.4 Sample Size Determination

The total number of subjects (200) is based on statistical calculation to have more than 80% power to detect a non-inferiority margin of 26 percentage points of the composite endpoint of acute rejection, graft loss and death over the baseline of 13% in the brand tacrolimus at one year post-transplantation. (See details in next paragraph.)

For power considerations regarding the primary objective, the following assumptions are made:

1. Subjects will be uniformly enrolled over 1-year accrual period
2. Primary analysis will be done via non-inferiority, log-rank tests on an intention-to-treat basis comparing generic recipients (Arm 2) with brand recipients (Arm 1)
3. Data will be also collected from standard-of-care records on subjects who are lost to follow-up
4. Overall, 13% of subjects are expected to experience the primary endpoint by 1 year post-transplant, yielding a yearly hazard rate for the reference group of  $-\log(0.87) = 0.14$

Given these assumptions, 200 subjects (if 50 and 150 in brand and generic groups, respectively) are needed to observe 25 events (6 and 19 in brand and generic groups, respectively). These numbers achieve >80% power at a 0.05 significance level to detect a non-inferiority hazard ratio of 3.54 when the actual hazard ratio is 1.0. PASS statistical software (version 13.0) was used for calculation. For completeness, we acknowledge that the study has 80% power only for the specific set of conditions listed above and may lack canonical power when analyzing hypotheses involving secondary endpoints.

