## **3 STUDY DESIGN AND EVALUATION**

### **3.1 Study Design**

A prospective, randomized, open-label, multicenter, parallel, observational study to compare the safety and efficacy of brand versus generic tacrolimus in 200 kidney transplant recipients over a one-year follow up period. All subjects will receive other immunosuppressive medications including induction therapy (thymoglobulin, basiliximab, or no induction) and maintenance, including mycophenolate mofetil and corticosteroid therapy as directed by standard-of-care at each center. Their medication information will be recorded in their study files.

The Phase 1 portion of this study consist of 2 Arms:

Arm 1: Brand Tacrolimus (Prograf) for entire study duration (12 months)

Arm 2: Generic Tacrolimus for entire study duration (12 months)

Additionally, the study consists of 2 Phases:

Phase 1: Subjects have been randomized into either Arm 1 or Arm 2 medication. Once 40 subjects have been enrolled onto Phase 1, Phase 2 will commence.

Phase 2: Subjects will no longer be randomized. All subjects will be enrolled onto generic tacrolimus because they have elected to receive generic tacrolimus (standard of care from the subject's insurance).

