**Table 1 - Via PASS**

Power  $\geq$  80% (alpha = 0.05, 5% dropout, 12 mo. study time)

| Scenario | Sample Size (N) | Brand Surv% (Haz rate/mo) | Equiv HR | Generic Non-inferior Surv% (hrate/mo) | 1-year Margin of inferiority |
|----------|-----------------|---------------------------|----------|---------------------------------------|------------------------------|
|          |                 |                           |          |                                       |                              |

|             |     |              |      |              |                   |
|-------------|-----|--------------|------|--------------|-------------------|
| Kidney only | 200 | 87% (0.0116) | 3.54 | 61% (0.0411) | $\Delta=26\%$ pts |
|-------------|-----|--------------|------|--------------|-------------------|

Source: PASS 13 Power Analysis and Sample Size Software (2014). NCSS, LLC. Kaysville, Utah, USA, [ncss.com/software/pass](http://ncss.com/software/pass). (Non-inferiority logrank test.)

A descriptive analysis will be incorporated of generic supplied within the analysis.

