#### **4.2 Statistical Analyses (Aim 1 only)**

The primary research hypothesis states that subjects receiving generic tacrolimus (Arm 2) would exhibit a 1-year survival rate non-inferior at a 26% margin to the rate among subjects receiving brand tacrolimus (Arm 1). The primary efficacy endpoint will be analyzed as time-to-event, with follow-up time measured in days, from the date of transplant to the date of composite endpoint. Statistical testing of time until composite event will be done for the intention-to-treat population. A Cox regression analysis (adjusting for transplant center via indicator variables) will be used to test the null hypothesis that  $H_0: HR \geq HR_0$  versus the alternative hypothesis  $H_1: HR < HR_0$  where  $HR_0$  is hazard ratio of the generic group over the brand group at the margin set at 3.54 (i.e., a 26% non-inferiority margin). The null hypothesis will be rejected if the upper bound of the 90% 2-sided confidence interval (corresponding to a 5% one-sided significance level) for HR is less than 3.54.

Secondary analyses are described next but all are considered exploratory since formal testing of hypotheses is considered dubious given the small sample sizes of stratified subjects. Additional Cox models that include indicator functions for the generic arm (with brand serving as baseline) and/or stratification based on age/race covariates will be used to estimate specific hazard ratios with 95% confidence intervals to evaluate differences among recipients in Arm 2 and risk groups. Also, individual analyses of single endpoint hazard ratios (graft rejection, failure, death) as well as point and interval estimates of group-specific survival rates at 1-year (via Kaplan-Meier and Greenwood methods) are planned without adjustment for multiple comparisons.

Standard descriptive summaries will also be used to report and compare adherence (as measured with daily medication diaries, and with the coefficient of variation of tacrolimus in subjects' blood) and immunologic endpoints (measured by the production of donor specific HLA antibodies).

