## 6.2 Study Therapy

**6.2.1 Clinical Sites:** Kidney recipients will be enrolled at UCLA, UCSD, UCI, UC Davis Medical Centers. Mechanistic studies will be performed utilizing specimens collected from all sites. Adherence will be measured with daily medication diaries, and with the coefficient of variation of tacrolimus in subjects' blood.

**6.2.2 References and comparator arms:** During phase 1 of study, following consent and randomization, the control group were prescribed brand tacrolimus and the comparator group was prescribed generic tacrolimus. The study drugs were prescribed upon discharge, but no later than 14 days after transplant. Subjects continued to receive study drug for up to one year post-transplant. During phase 2 of study, generic tacrolimus will only be prescribed as part of their regular care upon discharge but no later than 14 days after transplant.

**6.2.3 Provision of investigational drugs:** We anticipate that brand and generic tacrolimus will be provided for the entire study period for Phase 1 of the study. Generic tacrolimus will be obtained by the subject through their insurance for Phase 2 only. (See letters from Astellas - Appendix 5)

**6.2.4 Number of subjects and sample size justification:** We plan to enroll a total of 200 subjects between the four sites. Of the 200 kidney recipients at least 20 will be African American recipients. 40 randomized subjects will be on Brand and 160 subjects will be on generic.

**6.2.5 Eligible Subjects:** In Phase 1, eligible subjects will be initially randomized using a ratio of 2:1 (Brand:Generic) until 40 subjects have been enrolled into the brand medication arm (Arm 1) and 20 have been enrolled into the generic medication arm (Arm 2). In Phase 2, 140 additional eligible subjects will be enrolled without randomization onto generic tacrolimus only as part of their regular care. All subjects will be followed for 1-year post-transplant. (A split-phase randomization process is necessary due to a limited supply and narrow expiration-time window associated with the Brand medication product.)

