### **6.2.8 Study regimens:**

Eligible and consented subjects will be randomized into the 2 groups below:

Arm 1 (n=40) will receive brand tacrolimus for the entire study

Arm 2 (n=160) will receive generic tacrolimus for the entire study

According to their standard practice and attending physician and surgeon recommendation, subjects should also be on a maintenance regimen consisting of any of the following medications: mycophenolate mofetil, mycophenolate sodium, corticosteroids, azathioprine. Concomitant belatacept administration is not permitted. To minimize confounding factors, efforts will be made between UCSD, UCI, UC Davis, and UCLA to synchronize a similar organ specific maintenance immunosuppressive regimen across the four sites. However, each subject's maintenance regimen will ultimately be at the discretion of the treating physician. The tacrolimus level will be maintained between 4-11 ng/dL during the duration of the study.

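### The stated power above 80% is for a 50:150 split, but the plan enrols 40:160 and gives no power for it; Sections 3.1 and 6.2.5 also disagree on when Phase 1 ends

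*Combined protocol and SAP*

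**What the plan says.** Section 3.4 gives the power basis: "200 subjects (if 50 and 150 in brand and generic groups, respectively) are needed to observe 25 events", made up of 6 brand and 19 generic events. It continues: "These numbers achieve >80% power at a 0.05 significance level to detect a non-inferiority hazard ratio of 3.54", with a true hazard ratio of 1.0. It then limits the claim: "we acknowledge that the study has 80% power only for the specific set of conditions listed above". Table 1 repeats the result for N = 200 with 5% dropout and 12 months, and shows no allocation.

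The enrolment sections use another split. Section 6.2.4 says "40 randomized subjects will be on Brand and 160 subjects will be on generic". Section 6.2.5 builds the same totals from 40 brand and 20 generic subjects randomised 2:1 in Phase 1, plus 140 non-randomised generic subjects in Phase 2. Section 6.2.8 agrees: "Arm 1 (n=40) will receive brand tacrolimus for the entire study", with 160 in Arm 2.

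On the end of Phase 1, Section 3.1 says "Once 40 subjects have been enrolled onto Phase 1, Phase 2 will commence", whereas the Phase 1 counts in Section 6.2.5 add to 60.

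The decision rule is in Section 4.2: "The null hypothesis will be rejected if the upper bound of the 90% 2-sided confidence interval" for the hazard ratio is below 3.54, at a one-sided 5% level, from a Cox model adjusted for centre. The type of interval (Wald, score or likelihood-ratio) is not named.

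**The concern.** The power statement is tied to an allocation that the trial does not plan to enrol, and by the plan's own caveat it does not carry over to another one. Moving 10 subjects from brand to generic leaves the expected total of events unchanged under a true hazard ratio of 1. It removes events from the smaller arm, though, and that arm limits the precision of the hazard ratio. At stake is whether the primary non-inferiority test has the power that readers are told it has. The disagreement over when Phase 1 ends adds to this, because brand subjects are recruited only in Phase 1.

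**Working it through.** **Inputs.** Margin 3.54, true hazard ratio 1.0, 25 events, and 13% with the endpoint at one year (Section 3.4). 5% dropout over 12 months (Table 1). One-sided 5% level (Section 4.2; Section 3.4 does not state sidedness). Allocation 50:150 (Section 3.4) or 40:160 (Sections 6.2.4, 6.2.5 and 6.2.8). Exponential event and dropout times are my assumption.

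**Expected events.** The yearly event hazard is −ln 0.87 = 0.139 and the dropout hazard is −ln 0.95 = 0.051, which sum to 0.191. The probability of an observed event is (0.139/0.191) × (1 − 0.87 × 0.95) = 0.1268.
- 50:150 gives 6.3 + 19.0 events, which matches the plan's 6, 19 and 25.
- 40:160 gives 5.1 + 20.3 events, the same total with about one fewer in the brand arm.

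**Event formula.** Power = Φ(√(d·p·(1−p)) × ln 3.54 − 1.645), where d = 25, p is the brand fraction and ln 3.54 = 1.264.
- 50:150 (p = 0.25): √4.6875 = 2.165; 2.165 × 1.264 − 1.645 = 1.092; power 86.3%. This is consistent with the stated figure of more than 80%.
- 40:160 (p = 0.20): √4 = 2; 2 × 1.264 − 1.645 = 0.883; power 81.1%. The loss is about 5 points.

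By the same formula, 80% power needs (1.645 + 0.842)² / (p(1−p) × 1.264²) events: 20.6 at 50:150 and 24.2 at 40:160. With about 25 events expected, almost all the slack in the calculation is gone.

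A two-sided 0.05 reading gives 78.1% and 71.5%. It does not reproduce the plan's claim even at 50:150, so the one-sided reading is used.

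**Simulation of the Section 4.2 rule.** Exponential times, one year of follow-up, 5% dropout, true hazard ratio 1; success means that the upper 90% limit is below 3.54. The unadjusted models used 12,000 runs each and the centre-adjusted model 15,000. The Monte Carlo standard error is about 0.4 points.

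| Limit | 50:150 | 40:160 | Loss (points) |
|---|---|---|---|
| Wald | 78.4% | 72.9% | 5.5 |
| Wald, centre indicators (Table 2 site sizes, no centre effect) | 78.3% | 72.9% | 5.4 |
| Score | 79.7% | 74.1% | 5.6 |
| Likelihood-ratio | 74.7% | 67.8% | 6.9 |

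Without dropout each unadjusted figure rises by less than one point.

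**Two separate effects.** For the Wald limit, going from 86.3% (formula, 50:150) to 72.9% (simulation, 40:160) is 13.4 points. Of these, 7.9 arise at 50:150 from replacing the large-sample formula with the actual rule, and 5.5 come from the split.

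**End of Phase 1.** In Section 6.2.5, 40 + 20 = 60 randomised and 60 + 140 = 200. Section 3.1 read literally, with 2:1 randomisation, gives 40 × 2/3 ≈ 27 brand subjects. If the total stayed at 200, power would be 69.7% by the formula and 62-63% by simulation with a Wald limit.

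**The case against.** The strongest reply is that the plan claims only more than 80%, and the standard event formula still gives 81.1% at 40:160. On that formula the mismatch is an error of documentation and does not overturn the claim. That stands, and the split alone should not be said to push power below 80%.

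Most of the simulated shortfall is already present at 50:150, so it is a criticism of the approximation. That also stands, and the two effects are kept apart above. The result for the enrolled design does not change: the rule in Section 4.2 is below 80% at 40:160 with each interval type checked.

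The plan names PASS 13 and a non-inferiority log-rank test. PASS was not run here, so its own output for 40:160 is unknown. The Wald figure also assumes an interval type that Section 4.2 does not specify. At a true hazard ratio of 3.54 the Wald and score rules reject in about 6% of simulated trials, against about 5% for the likelihood-ratio rule. This argues for reporting a range, but it does not help the stated power, because the rule closest to its nominal level has the lowest power.

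Finally, 40 brand subjects appear in three sections whose totals agree, so the sentence in Section 3.1 may be a slip. That is fair, and the 27-brand scenario should carry little weight. The two passages still conflict.

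**Conclusion.** The concern holds. The power statement in Section 3.4 describes 50:150, the plan enrols 40:160, and no power is given for the planned split. The split costs about 5 points by the event formula (86.3% to 81.1%) and 5 to 7 points by simulation. Under the Section 4.2 rule, power at 40:160 is about 73% with a Wald limit and 68-75% across interval types, partly from the split and partly from the optimism of the formula with so few brand events. These figures rest on a 13% one-year event rate, a true hazard ratio of 1, exponential times and a one-sided 5% level. The conflict between Sections 3.1 and 6.2.5 (40 against 60 subjects in Phase 1) is real, though probably a wording slip. The point should be fixed; it does not invalidate the primary analysis.

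**What to change.** 1. Recompute Section 3.4 and Table 1 for 40:160, with about 5 brand and 20 generic events. If Phase 1 has closed, as the past tense in Sections 6.2.2 and 6.2.7 suggests, use the brand count actually randomised.
2. State the power of the planned Cox rule alongside any formula result, and name the method used for each. On the assumptions above this is about 73% for a Wald limit and 68-75% across interval types.
3. Name the interval type in Section 4.2.
4. Reconcile Section 3.1 with Section 6.2.5 against the actual Phase 1 count.

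The cost is protocol and SAP wording only. Correcting the statement requires no added enrolment, but the stated power becomes less favourable.

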**Table 1 - Via PASS**

Power  $\geq$  80% (alpha = 0.05, 5% dropout, 12 mo. study time)

| Scenario | Sample Size (N) | Brand Surv% (Haz rate/mo) | Equiv HR | Generic Non-inferior Surv% (hrate/mo) | 1-year Margin of inferiority |
|----------|-----------------|---------------------------|----------|---------------------------------------|------------------------------|
|          |                 |                           |          |                                       |                              |

|             |     |              |      |              |                   |
|-------------|-----|--------------|------|--------------|-------------------|
| Kidney only | 200 | 87% (0.0116) | 3.54 | 61% (0.0411) | $\Delta=26\%$ pts |
|-------------|-----|--------------|------|--------------|-------------------|

Source: PASS 13 Power Analysis and Sample Size Software (2014). NCSS, LLC. Kaysville, Utah, USA, [ncss.com/software/pass](http://ncss.com/software/pass). (Non-inferiority logrank test.)

A descriptive analysis will be incorporated of generic supplied within the analysis.

### 3.5 Data Safety and Monitoring Board Review Responsibilities

A Data and Safety Monitoring Board (DSMB) will be convened for only Phase 1 of the study trial, to act in an advisory capacity to monitor participant safety, evaluate the progress of the study, review procedures for maintaining the confidentiality of data, and review the quality of data collection, management, and analyses. The DSMB will include 3 people with no interest or participation in research activities associated with this trial. DSMB members will not have any direct involvement with the study investigators or intervention. Each DSMB member will sign a Conflict of Interest Statement which includes current affiliations, if any, with pharmaceutical and biotechnology companies (e.g., stockholder, consultant), and any other relationships that could be perceived as a conflict of interest related to the study objectives. Members of the Board will include experts in subject education, cultural tailoring, randomized controlled trials, and kidney transplantation.

The Board will be instructed to review the study and its educational components to look for any component of the design or education that could result in harm of study participants. Data will be presented in a blinded manner during the open sessions of the DSMB. At DSMB meetings, data and discussion are confidential. There will be no DSMB for Phase 2 of the study. This is because the Phase 2 part of the study is open label, where standard of care procedures are being performed. There will be no use of any investigational drug. The Principal investigator will continue to monitor participant safety per study site standard of care guidelines.

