### 3.6 Interim Analyses

There will be no interim analysis on the primary endpoint. Safety analyses of secondary safety endpoints will be performed monthly and reviewed by The Data and Safety Monitoring Board (DSMB) for Phase 1 of the study. Safety endpoints and SAEs will be monitored on a continuous basis.

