## 6.4 Blinding/Unblinding

As this is an open label study, no arrangements need to be made for blinding or potential unblinding.

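### Section 3.1 ends randomization at 40 subjects and section 6.2.5 at 60; only 60 fits the planned arms, and the DSMB's remit hangs on the same undefined Phase 1

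*Combined protocol and SAP*

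**What the plan says.** **When Phase 1 ends.** Section 3.1 says "Once 40 subjects have been enrolled onto Phase 1, Phase 2 will commence", and that subjects are no longer randomized from then on. Section 6.2.5 says that "eligible subjects will be initially randomized using a ratio of 2:1 (Brand:Generic") and that this continues "until 40 subjects have been enrolled into the brand medication arm (Arm 1) and 20 have been enrolled into the generic medication arm", after which 140 more subjects receive generic tacrolimus without randomization. Sections 6.2.4 and 6.2.8 give the arms as 40 brand and 160 generic.

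**What the DSMB covers.** Section 3.5: "A Data and Safety Monitoring Board (DSMB) will be convened for only Phase 1 of the study trial". Section 3.6 has monthly safety analyses "reviewed by The Data and Safety Monitoring Board (DSMB) for Phase 1 of the study". Neither section gives a date or event at which the Board's work is complete.

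**Why Phase 2 has no Board.** Section 3.5: "There will be no DSMB for Phase 2 of the study. This is because the Phase 2 part of the study is open label". The passage goes on to give two further grounds, namely that procedures are standard of care and that no investigational drug is used. It leaves Phase 2 safety monitoring with the principal investigator.

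**The concern.** The number that ends Phase 1 is an operating trigger. It decides when randomization stops and so how many brand subjects the trial will ever have, because Phase 2 adds none. Two sections give different numbers. A site working from section 3.1 could stop a third short of the planned brand arm, and brand is the smaller arm, which limits the precision of the hazard ratio.

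The DSMB's remit rests on the same label. Phase 1 can mean an enrolment stage, or the randomized cohort through its year of follow-up. Phase 1 subjects are still being followed while Phase 2 enrols, so the two meanings give very different amounts of Board review, and the protocol does not choose between them.

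**Working it through.** **1. Which trigger fits the stated arms**

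- Section 6.2.5: 40 brand + 20 generic = 60 in Phase 1. Adding 140 gives 20 + 140 = 160 generic and 40 + 160 = 200 in total. This reproduces sections 6.2.4 and 6.2.8 exactly.
- Section 3.1: 40 subjects at 2:1 gives 40 × 2/3 = 26.7 brand and 13.3 generic. Brand falls short of 40 by one third. Keeping 140 in Phase 2 gives 40 + 140 = 180, not 200. Keeping 200 gives about 173 generic, not 160.

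**2. Effect on power**

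Inputs from sections 3.4 and 4.2: 25 events, margin HR 3.54, true HR 1.0, one-sided 5% level. With brand fraction p and d events, the Schoenfeld approximation is

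power = Φ(√(d·p·(1−p)) × ln 3.54 − 1.645), with ln 3.54 = 1.264.

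| Brand / generic | p | √(d·p·(1−p)) | × 1.264 | Power |
|---|---|---|---|---|
| 50 / 150 (section 3.4) | 0.250 | 2.165 | 2.737 | 86% |
| 40 / 160 (sections 6.2.4, 6.2.8) | 0.200 | 2.000 | 2.528 | 81% |
| 26.7 / 173.3 (section 3.1, total 200) | 0.133 | 1.700 | 2.149 | 69% |

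The first row agrees with the protocol's claim of more than 80%. The second still meets it; the third does not. Rounding brand up to 27 gives 69.7%. If Phase 2 stays at 140, so that the total is 180 and events scale to 25 × 180/200 = 22.5, power is also about 69%.

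**3. What the DSMB sees under each meaning of Phase 1**

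- *Cohort followed to the end:* all randomized follow-up is reviewed.
- *Enrolment stage only:* under the uniform 12-month accrual of section 3.4 (200/12 = 16.7 per month), 60 subjects take 3.6 months and have mean follow-up of 1.8 months when Phase 2 opens. That is 60 × 1.8 = 108 of 60 × 12 = 720 subject-months, or 15%. With 40 subjects it is 2.4 months, mean 1.2, so 48 of 480, or 10%.

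The text favours the cohort meaning. Section 3.1 describes the Phase 1 arms as lasting 12 months, section 6.2.3 supplies drug to Phase 1 for the whole study period, and section 6.2.9 still uses the label at the month 12 drug return.

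**4. Generic subjects without DSMB review**

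140/160 = 87.5% of the generic arm, and 140/200 = 70% of all subjects.

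**5. The grounds for having no Phase 2 Board**

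- *Open label:* this does not separate the phases. Section 6.4 says of the whole study "As this is an open label study, no arrangements need to be made for blinding".
- *No investigational drug:* the synopsis, under statistical methods, counts both brand and generic tacrolimus as investigational drug, so the two passages disagree.
- *Standard-of-care procedures:* Phase 2 does differ in being non-randomized with insurance-supplied drug. But its 140 subjects are most of the generic arm in the main comparison.

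**The case against.** The 40 in section 3.1 may simply be shorthand for 40 brand subjects, and the arithmetic elsewhere settles the matter. That makes the correction easy, but does not make section 3.1 correct as it stands. Sections 6.2.2 and 6.2.7 also describe Phase 1 partly in the past tense, so enrolment may have closed. If so, the power figures for the 40-subject trigger apply only if that trigger was used, and the remedy is to report the actual number.

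A reader might infer three stronger points that the documents do not support.

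- *Phase 2 is unreviewed.* It lacks DSMB review only. Section 3.5 keeps investigator monitoring, section 3.6 has continuous monitoring of safety endpoints and SAEs, and section 9.3 provides for reports to IRBs and SAE reports to the FDA with quarterly aggregates. None of these is described as an independent comparison by arm.
- *Most randomized follow-up escapes the Board.* This needs the enrolment-stage meaning, which is the less likely one. The 10% and 15% above show what the ambiguity could cost; they do not show a loss.
- *The only reason for having no Phase 2 Board is that it is open label.* Two other grounds are given, and the non-randomized, insurance-supplied setting is a real difference.

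It is also fair to say that putting self-selected Phase 2 subjects into DSMB tables by arm would mix randomized and non-randomized comparisons. Whether the larger numbers justify that is debatable.

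**Conclusion.** The conflict between sections 3.1 and 6.2.5 is an error as written. Only 60 Phase 1 subjects fit the 40/160 arms. Stopping at 40 would leave about 27 brand subjects and power of about 69% instead of about 81%. These figures assume 25 events, 200 subjects, a true hazard ratio of 1.0, exact 2:1 allocation and the Schoenfeld approximation. They treat the pooled arms as the protocol's primary analysis does.

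The unstated end of DSMB review is an ambiguity that should be closed, not a demonstrated gap in oversight. That 140 of 160 generic subjects have no DSMB review is a fact of the design. The grounds offered for it are partly inconsistent with section 6.4 and the synopsis, but extending the Board to Phase 2 remains a judgement for the sponsor.

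**What to change.** 1. In section 3.1, state that Phase 2 starts after 40 brand and 20 generic subjects (60) have been randomized. If Phase 1 enrolment has closed, state the number actually randomized to each arm.
2. In section 3.5, with a matching phrase in section 3.6, state that the Board reviews the Phase 1 cohort until its last subject's month 13 safety call, whenever Phase 2 enrolment begins.
3. In section 3.5, reconcile the grounds for having no Phase 2 Board with section 6.4 and with the synopsis definition of investigational drug. If the sponsor keeps Phase 2 outside the Board's remit, give reasons that do distinguish it from Phase 1.

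The cost is a short text amendment. Item 2 may add some further meetings of the existing three-member Board. No visit, procedure or assessment is added.
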